1.3.4 Ototoxicity

Cisplatin causes dose- and schedule-dependent permanent, sensorineural hearing loss by damaging cochlear hair cells.⁸⁷ Initially, osteosarcoma patients experience high frequency hearing loss at 4 to 8 kHz at cumulative doses exceeding 300 mg/m², but hearing at lower frequencies becomes impaired as the cumulative dose increases, and a substantial fraction of patients are affected.^{14,88-90} Younger patients are at greater risk for hearing loss from cisplatin.^{91,92} With long-term follow-up, there may be worsening or progression of hearing loss at lower frequencies.⁹³

Fractionating the cisplatin dose appears to lessen the risk of ototoxicity,⁸⁸ but more effective strategies to prevent damage to the hair cells are needed. Sodium thiosulfate is being tested as a rescue agent in an ongoing COG trial, but thiosulfate is a non-selective rescue agent and can interfere with the anti-tumor effect of cisplatin. Cochlear hair cells also express OCT2, and inhibition of OCT2 during cisplatin therapy may selectively block the uptake of cisplatin into hair cells without impacting the drug's anti-tumor effect.^{48,50}

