6.1 Statistical Analysis Plan

6.1.1 Primary Endpoints

- **Urinary KIM-1, NAG and NGAL** will be normalized to the urinary creatinine concentration measured in the same urine specimen and expressed as ng/mg Cr. The end of infusion and 7-day post values for each biomarker will be analyzed by course for cisplatin with vs. without pantoprazole and by dose for HDMTX administered as a 4 h vs. 12 h infusion.
- **GFR** will be estimated from serum creatinine and from the cystatin C (see Section 1.3.3) prior to each course of cisplatin and each dose of HDMTX and 7-days post treatment. A decrease in the GFR will reflect toxicity from the immediately preceding course of

Protocol number: CHP12ST051
Amendment number:
Version date: April 2, 2013

cisplatin or dose of HDMTX. Change in GFR will be analyzed by course for cisplatin with vs. without pantoprazole and by dose for HDMTX administered as a 4 h vs. 12 h infusion.

- Change in **FEMg** from pre-dose 1 (day 1 of cycles 1-4) of cisplatin to pre-dose 2 (day 2 of cycles 1-4) of cisplatin and day 7 will be measured for each cycle containing cisplatin (n=4). Change in FEMg will be analyzed by course for cisplatin with vs. without pantoprazole to assess renal tubular toxicity.
- The **urinary MTX concentration** at the end of each HDMTX infusion on cycles 1-4 will be tabulated for the 4 and 12 h infusion durations and compared to the MTX solubility limit for the urine pH to determine whether the solubility limit was exceeded. End infusion urine MTX concentration will also be correlated with simultaneous serum concentration and with the severity of renal toxicity as measured by AKI biomarkers and serum creatinine and serum cystatin C.
- An **audiogram** will be performed prior to Cycles 1, 2, 3 and 4 and at the end of therapy (after cycle 6). The average hearing level (HL) threshold in dB over the frequency range of 4,000-8,000 Hz will be derived separately for each ear from each audiogram. The increase in the average HL threshold in dB from the pre-cycle 1 to pre-cycle 2, from pre-cycle 2 to pre-cycle 3, from pre-cycle 3 to pre-cycle 4, and from pre-cycle 4 to end of therapy audiograms will be derived and this increase in HL threshold will be compared for cisplatin with vs. without pantoprazole.

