For each primary endpoint, we will construct separate models for comparison of cisplatin with vs. without pantoprazole and for comparison of the 4 vs. 12 h infusion durations of HDMTX. Linear mixed effects model will be used for this crossover design, including all repeated measures as the outcome, order type and period number as the fixed effects, and a subject level random intercept to account for within-subject correlation (or unstructured correlation matrix for the repeated measures if needed). Appropriate contrasts will be constructed to test for treatment effect. For nephrotoxicity outcomes using AKI biomarkers, little carryover effect is expected. For ototoxicity outcomes, carryover effect is possible, but unlikely to be differential between comparison arms because we randomized the order of treatment. Nevertheless, we will conduct a statistical test for differential carryover effect, acknowledging limited power with this test. If differential carryover is present in the analysis we will only use the data from cycle 1.

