- For comparison of HDMTX infusion durations, each patient will have 4 doses with 4 h infusion duration and 4 doses with 12 h infusion duration. Using the Wilks Lambda test with a significance level of 0.05 under the framework of general linear models, with 24 subjects of 8 repeated measures (4 measures with 4 h duration and 4 measures with 12 h duration), we will have 80% power to detect a 0.42SD difference assuming a within-subject correlation of 0, and will detect a 0.30SD difference assuming a correlation of 0.5.
- For the analyses of ototoxicity data (hearing level thresholds from 4 to 8 kHz in dB), treatment cycle will be the analysis unit. Each patient will have 2 cycles with pantoprazole and 2 cycles without pantoprazole. Using the Wilks Lambda test with a significance level of 0.05 under the framework of general linear models, with 24 subjects of 4 repeated measures (2 measures with and 2 measures without pantoprazole), we will have 80% power to detect a 0.60SD difference assuming a within-subject correlation of 0, and will detect a 0.42SD difference assuming a correlation of 0.5. Moreover, if differential carryover is present, we will only use the data from the first two cycles, so that the comparison will be between subjects, with 12 subjects in each comparison group. We will then have 80% power to detect a 1.2SD difference, based on a two-sided, two-sample t test with a significance level of 0.05.

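### The between-patient hearing fallback is powered as an unadjusted t test with no covariates named, although baseline threshold and age are collected; the gain from adjusting depends on a variance share the plan does not give

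*Combined protocol and SAP*

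**What the plan says.** Section 6.2 plans for differential carryover in the hearing data by moving to a between-patient comparison "with 12 subjects in each comparison group". Its power statement reads: "We will then have 80% power to detect a 1.2SD difference, based on a two-sided, two-sample t test", at a significance level of 0.05. No covariate is mentioned.

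Section 6.1.1 says the audiogram "will be performed prior to Cycles 1, 2, 3 and 4 and at the end of therapy". The outcome is a change between successive audiograms, starting with "The increase in the average HL threshold in dB from the pre-cycle 1 to pre-cycle 2". The mixed model for the crossover has order and period as its only fixed effects. For the fallback the section says: "If differential carryover is present in the analysis we will only use the data from cycle 1". It names no test and no covariates for that case. Section 6.2 instead restricts the fallback to the first two cycles.

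Both candidate covariates are available. Section 3.1.1 requires a baseline audiogram before cisplatin, and section 3.4.1 records demographic data at enrolment. Section 1.3.4 states: "Younger patients are at greater risk for hearing loss from cisplatin". Section 3.4.2 admits any age under 30 and limits hearing-evaluable patients to thresholds of 25 dB or less at all frequencies. Section 3.2 balances the four arms within each set of 12 patients but does not stratify by age.

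**The concern.** In the crossover each patient is his or her own control, so age and baseline hearing largely cancel. In the fallback they do not. It is also the hearing analysis with the least information: 1.2 SD detectable, against 0.42 to 0.60 SD for the crossover in section 6.2.

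Baseline threshold then enters only by subtraction, and age does not enter at all. With 12 patients per group and a wide age range, a chance age difference in the one trial actually run would feed into the pantoprazole estimate. If covariates are not fixed in advance, they would be chosen after the carryover test has been seen.

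**Working it through.** **Inputs from the documents.** n = 12 per group, difference d = 1.2 SD, two-sided alpha 0.05, two-sample t test (section 6.2). All 12 per group are taken to be evaluable for hearing.

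**Input not in the documents.** R², the share of variance in threshold change explained by baseline threshold and age together. It is varied from 0 to 0.30.

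**Step 1: the plan's own figure.** Degrees of freedom are 2 × 12 − 2 = 22. The noncentrality is 1.2 / √(2/12) = 2.94. The noncentral t distribution gives power 80.2%, and 80% power is reached at 1.197 SD. The stated figure reproduces.

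**Step 2: adjustment for two covariates.** Regressing the post-treatment threshold on treatment with the pre-cycle-1 threshold as covariate gives the same treatment estimate as regressing the change with that covariate. R² can therefore be expressed on the change scale, where the plan's SD lies. Three things alter:

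- the residual SD becomes √(1 − R²);
- the degrees of freedom become 22 − 2 = 20;
- chance covariate imbalance inflates the variance by about 1 + 2/(21 − 2) = 1.105.

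The noncentrality is 1.2 / [√(1 − R²) × √(2/12) × √1.105].

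| R² (assumed) | Noncentrality | Power at 1.2 SD | Simulated power | Difference at 80% power |
|---|---|---|---|---|
| 0 | 2.80 | 75.8% | 75.9% | 1.26 SD |
| 0.10 | 2.95 | 80.0% | 80.1% | 1.20 SD |
| 0.20 | 3.13 | 84.4% | 84.4% | 1.13 SD |
| 0.30 | 3.34 | 88.8% | 89.2% | 1.06 SD |

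The simulations used 40,000 trials per point. Adjustment breaks even with the t test at R² of about 0.10.

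**Step 3: what baseline alone could contribute.** Let ρ be the correlation of pre- and post-treatment thresholds and r the ratio of post- to pre-treatment SD. The adjusted variance relative to the change score is r²(1 − ρ²) / (r² + 1 − 2ρr). All values of ρ and r below are assumptions. The power figures are for the two-covariate model with age explaining nothing, at ρ = 0.5.

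| r | Variance ratio | Power at 1.2 SD |
|---|---|---|
| 1 | 0.75 / 1 = 0.75 | 86.7% |
| 1.25 | 1.172 / 1.3125 = 0.89 | 80.4% |
| 1.5 | 1.6875 / 1.75 = 0.96 | 77.3% |
| 2 | 3 / 3 = 1.00 | 75.8% |

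With equal SDs the ratio reduces to (1 + ρ)/2, and break-even lies near ρ = 0.8. At ρ = 0.9 power is 77.9%.

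**The case against.** The strongest case against is that this is an efficiency preference within a contingency. The fallback is reached only through a carryover test that section 6.1.1 itself describes as having limited power. Randomisation makes the unadjusted comparison unbiased, so a reader who infers that the t test is biased goes too far. Chance imbalance affects the single realised estimate, and its expected effect is already in the standard error.

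The gain may also be absent. Baseline spread is restricted by the 25 dB limit, and cisplatin may widen the spread afterwards. Step 3 shows that modest widening removes the benefit of baseline, so age would have to supply it.

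Finally, the t test appears only as the basis of a power calculation. Section 6.1.1 neither commits to it nor excludes covariates, so the unadjusted analysis is an inference from section 6.2.

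All of this stands. It limits the size of the gain, but the fallback analysis remains unspecified, and the covariates are still best named before the data are seen.

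**Conclusion.** The point holds as a low-cost improvement. The fallback is powered without adjustment, its analysis names no covariates, and two covariates already in hand are plausible candidates, one of them a risk factor the protocol itself names.

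A reader might infer that adjustment lifts power from 80% to about 88% and lowers the detectable difference to about 1.07 SD. The documents do not support this. Those figures charge for baseline alone and need a pre/post correlation of 0.5 with equal SDs. The 0.5 in section 6.2 is a correlation among the crossover's repeated measures, and nothing is said about the SDs. With both covariates and uninformative age, the same assumptions give 86.7%.

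The supportable statement is conditional: about 76%, 80%, 84% or 89% power at 1.2 SD if the two covariates explain 0, 10%, 20% or 30% of the variance in threshold change. Since the low end is below 80%, 1.2 SD is a reference for the unadjusted test and not a worst-case bound.

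**What to change.** 1. Reconcile sections 6.1.1 (cycle 1 only) and 6.2 (first two cycles). This decides whether the pre-cycle-2 or the pre-cycle-3 audiogram supplies the outcome, and the model cannot be written until it is settled.
2. In both sections, prespecify the fallback as a linear model of the post-treatment 4-8 kHz threshold on pantoprazole (yes or no), with pre-cycle-1 threshold and age at enrolment as covariates.
3. Keep 1.2 SD as the unadjusted reference. Beside it, give adjusted power over an assumed range of R², labelled as an assumption. Do not replace 1.2 SD with a single smaller figure.

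The cost is a few lines of text and no new data. The statistical price is two of the 22 degrees of freedom and a loss of up to about 4 points of power (80.2% − 75.8% = 4.4) if the covariates explain nothing.

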6.3 Interim Analysis

The sample size in this pilot study is too small to derive a statistically valid stopping rule with sufficient sensitivity. However, after the first 12 patients have completed treatment, the investigators will evaluate the following parameters to determine whether pantoprazole or prolonging the HDMTX infusion affect toxicity or anti-tumor response to MAP:

- The incidence and severity (CTCAE grade) of toxicities will be compared for

Protocol number: CHP12ST051
Amendment number:
Version date: April 2, 2013

cisplatin/doxorubicin with vs. without pantoprazole and for HDMTX infused over 4 h vs. 12 h within and across patients.

- Radiographic response (log ratio) and histological response (% tumor necrosis) following 2 cycles of neoadjuvant chemotherapy will be compared in patients who received pantoprazole vs. patients who did not receive pantoprazole and in patients who received HDMTX over 4 h vs. 12 h.

If the toxicity from MAP is clinically significantly worse when cisplatin is administered with pantoprazole or when HDMTX is infused over 12 h OR if radiographic or histological response to neoadjuvant chemotherapy is clinically significantly less in patients receiving pantoprazole or a prolonged HDMTX infusion, then the intervention found to have the worse outcome will be discontinued.

7. STUDY MEDICATIONS

All medications prescribed in this protocol are commercially available. The MAP chemotherapy regimen, which includes cisplatin, doxorubicin and methotrexate, is the standard of care for osteosarcoma, and the doses, routes of administration and schedules are also standard, except for the alternative infusion duration for HDMTX. Intravenous pantoprazole is being studied to determine whether co-administration with cisplatin can selectively prevent cisplatin nephrotoxicity and ototoxicity.

7.1 Intravenous Pantoprazole (PROTONIX I.V.)

- **IUPAC Name:** (RS)-6-(Difluoromethoxy)-2-[(3,4-dimethoxypyridin-2-yl)methylsulfinyl]-1H-benzo[d]imidazole
- **Molecular formula & weight:** C₁₆H₁₅F₂N₃O₄S - 383.4 g/mol (Fig 5, chemical structure)
- **Manufacturer:** Pfizer Injectables (Distributed by Wyeth Pharmaceuticals Inc.)
- **Drug supply:** purchased from commercial sources
- **Indications:** gastroesophageal reflux associated with a history of erosive esophagitis and pathological hypersecretory conditions (e.g., Zollinger-Ellison syndrome)
- **Dosage forms and strength:** supplied in a vial containing 40 mg of pantoprazole as a freeze dried powder
- **Storage and Handling:** store vials at 20-25°C (USP controlled room temperature); excursions permitted to 15-30°C.
- **Dosing (Section 3.1.3):** 0.3 mg/kg IV over 15 min immediately prior to each dose of cisplatin as a loading dose followed by 1.3 mg/kg IV infused over 4 h concurrent with each 4 h cisplatin infusion on either Cycles 1 & 2 OR Cycles 3 & 4 depending on the treatment arm. See Section 1.3.8 for the rationale for pantoprazole administration schedule.
- **Compatibility:** the compatibility of the cisplatin and pantoprazole drugs solutions was

Protocol number: CHP12ST051
Amendment number:
Version date: April 2, 2013

tested at UPenn by [name], and at the concentrations used for drug administration, there was no evidence of an interaction – indicating that the pantoprazole solution can be infused into the same intravenous tubing through which the cisplatin is being infused.

- **Clinical pharmacology:** see Section 1.3.5 for pediatric pharmacokinetic data and tolerability of single doses in children
- **Adverse reactions:** reactions reported in clinical trials in adults (n=1473) with GERD at a frequency >2% included headache (12%), diarrhea (8.8%), nausea (7%), abdominal pain (6.2%), vomiting (4.3%), flatulence (3.9%), dizziness (3%), arthralgia (2.8%). The use of PPIs is associated with a moderately increased risk of *C. difficile* colitis.^{113,114}
- **Drug accountability:** a separate drug supply will be purchased for this study using the research funds, and NCI DARFs will be used to track drug supply.
- **IND status:** this pilot study will evaluate pantoprazole for a non-approved indication. The use of pantoprazole in this study meets the five criteria for IND exempt status:
 - The study is not intended to support FDA approval of a new indication or a significant change in the product labeling
 - The study is not intended to support a significant change in the advertising for the product
 - The investigation does not involve a route of administration or dosage level or use in a patient population or other factor that significantly increases the risk (or decreases the acceptability of the risks) associated with the use of the drug product
 - The study is conducted in compliance with institutional review board (IRB) and informed consent regulations set forth in 21 CFR parts 56 and 50
 - The study is conducted in compliance with § 312.7 (promotion and charging for investigational drugs)

8. SAFETY MANAGEMENT

Patients with osteosarcoma that will be treated with surgery (or radiation if surgery is not feasible) and a standard 3-drug MAP chemotherapy will be enrolled on this pilot trial to assess two interventions designed to reduce the nephrotoxicity and ototoxicity from cisplatin and HDMTX. The primary endpoints on this trial will monitor the incidence and severity of these known toxicities. Secondary endpoints include monitoring the overall toxicity of the regimen and response to neoadjuvant chemotherapy to determine whether the interventions increase the incidence or severity of the other expected toxicities of the regimen or alter the response to neoadjuvant treatment. Toxicities of the regimen will be categorized and graded according to the standard NCI CTCAE v.4 toxicity criteria.

Protocol number: CHP12ST051
Amendment number:
Version date: April 2, 2013

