3.1.5 Dose Modifications

Modification of the doses of cisplatin, doxorubicin, and HDMTX is required if toxicity for the drugs exceeds the thresholds listed in the Tables below on a prior treatment cycle. The percent of full protocol prescribed dose should be recorded on the TDM in the column labeled “% Dose”. If the dose is reduced by 25%, then the % Dose should be recorded as 75% (75% of the full dose).

Cisplatin:

Toxicity	Severity	Modification
Ototoxicity	>30 dB threshold at 2 kHz	Discontinue cisplatin
Nephrotoxicity	Serum creatinine >ULN for age and gender OR creatinine clearance <70 mL/min/1.73 m ²	Hold cisplatin until criterion in Section 3.1.4 is met
Neuropathy*	Grade >2 motor or sensory neuropathy	Hold cisplatin until resolved to grade ≤2

* See Appendix 2 for toxicity grading scale

Doxorubicin:

Toxicity	Severity	Modification
Myelosuppression	Planned day 22 HDMTX is delayed by >10d (cycle day >32) due to ANC <250/mcL or platelet count <50,000/mcL	Reduce doxorubicin dose by 20%
Cardiotoxicity	SF <27% (confirmed with repeat Echocardiogram 1 week later)	Hold doxorubicin until recovery to SF >28%
Mucositis	Grade 4 related to doxorubicin	Reduce doxorubicin dose by 20%

HDMTX:

Toxicity	Severity	Modification
Nephrotoxicity	Serum creatinine >ULN for age and gender OR creatinine clearance <70 mL/min/1.73 m ²	Hold HDMTX. Omit dose if renal function has not recovered after a 7-day delay
Mucositis	Grade 4 related to HDMTX	Reduce HDMTX by 50%

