6. STATISTICAL CONSIDERATIONS

This is a pilot study to evaluate pharmacologically-based dosing approaches to prevent the nephrotoxic effects of HDMTX and cisplatin and ototoxic effect of cisplatin in children, adolescents and young adults with osteosarcoma treated with the standard MAP chemotherapy regimen. Acute biomarkers of AKI (KIM-1, NAG, NGAL) and renal function tests (creatinine, cystatin C, FEMg) will be used to assess the incidence and severity of nephrotoxicity after each course of cisplatin (with and without pantoprazole) and HDMTX (infused over 4 and 12 h), and audiograms will be used to measure hearing loss prior to cycles 1-4 and at the end of therapy.

A 2 x 2 factorial, randomized crossover design will allow patients to serve as their own control. Nephrotoxicity data will be analyzed by course for cisplatin and by dose for HDMTX, and ototoxicity data will be analyzed by treatment cycle. All endpoints will be analyzed as continuous variables.

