6.1.2 Secondary Endpoints

- **Common grade ≥ 2 toxicities** from cisplatin + doxorubicin (other than cisplatin nephrotoxicity and ototoxicity), including myelosuppression, mucositis, nausea and vomiting leading to dehydration requiring IV fluid hydration, peripheral neuropathy, cardiac dysfunction, and treatment delays due to toxicity will be collected and graded according to CTCAE v.4. Similarly, HDMTX-related grade ≥ 2 toxicities (other than nephrotoxicity), including myelosuppression, mucositis, dermatitis, hepatotoxicity and neurotoxicity will be collected and graded. The incidence and severity (grade) of toxicities will be tabulated and compared by treatment arm (with vs. without

pantoprazole for cisplatin + doxorubicin and by infusion duration for HDMTX).

- **Response** to 2 cycles of neoadjuvant chemotherapy will be assessed radiographically and histologically.
 - The volume of the tumor on MRI will be measured pretreatment and pre-operatively (post-cycle 2). The log ratio (Section 5.2) of the two measurements will be derived and compared using a non-parametric analysis for cisplatin with (patients on treatment arms 1 and 3) vs. without (patients on treatment arms 2 and 4) pantoprazole and for HDMTX administered as a 4 h infusion (treatment arms 1 and 2) vs. a 12 h infusion (treatment arms 3 and 4).
 - The tumor specimen that is removed after 2 cycles of neoadjuvant chemotherapy will be evaluated histologically and the percent of the tumor that is necrotic will be estimated from review of multiple sections. The percent necrosis will be compared using a non-parametric analysis for cisplatin with (patients on treatment arms 1 and 3) vs. without (patients on treatment arms 2 and 4) pantoprazole and for HDMTX administered as a 4 h infusion (treatment arms 1 and 2) vs. a 12 h infusion (treatment arms 3 and 4).
- **GFR** estimated from serum creatinine using the modified Schwartz formula will be correlated with GFR estimated from serum cystatin C (Section 1.3.3, the equation also includes serum creatinine and BUN). The presence and amount (normalized to creatinine concentration) of biomarkers of AKI in urine will be correlated with proteinuria, serum creatinine, and change in FEMg.

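### The plan promises the incidence of nephrotoxicity and ototoxicity, but it compares treatments only on continuous values and leaves both out of the final graded toxicity tables

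*Combined protocol and SAP*

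**What the plan says.** - **Section 8, Safety Management**, on nephrotoxicity and ototoxicity: "The primary endpoints on this trial will monitor the incidence and severity of these known toxicities".
- **Section 6, opening**, on the biomarkers and renal function tests: they "will be used to assess the incidence and severity of nephrotoxicity after each course of cisplatin", and likewise after HDMTX. The next paragraph adds: "All endpoints will be analyzed as continuous variables".
- **Section 6.1.1** defines creatinine-normalised urinary biomarkers, change in estimated GFR (before each course or dose and 7 days after), change in FEMg, end-of-infusion urine MTX, and the mean 4-8 kHz hearing threshold. For the audiogram, "this increase in HL threshold will be compared for cisplatin with vs. without pantoprazole". The model is: "Linear mixed effects model will be used for this crossover design, including all repeated measures as the outcome".
- **Section 6.1.2** tabulates and compares graded toxicities by treatment, but covers those "from cisplatin + doxorubicin (other than cisplatin nephrotoxicity and ototoxicity" and, for HDMTX, "toxicities (other than nephrotoxicity), including myelosuppression, mucositis, dermatitis, hepatotoxicity and neurotoxicity".
- **Section 5.2** makes the Section 5.4 events a secondary endpoint. The tracked list in 5.4 names no renal or hearing event. It does include treatment delays, missed doses and dose modifications for toxicity.
- **Section 3.1.5** sets creatinine thresholds for holding cisplatin and HDMTX and, for stopping cisplatin, a hearing criterion of ">30 dB threshold at 2 kHz".

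**The concern.** The two toxicities that the trial is meant to prevent are the ones taken out of the final graded tables. A mean difference cannot show whether a benefit comes from a small shift in every course or from avoiding a few badly injured ones. Section 1.3.2.1 describes serious HDMTX kidney injury as uncommon: 1.8% severe, and delayed excretion in 5% of courses at the site. Section 1.3.2 says MTX can alter filtration transiently, so an acute creatinine peak may have recovered by the 7-day GFR estimate. Section 6.2 says the study should yield a signal that justifies a randomised trial; whoever plans that trial will want event counts as well as mean shifts.

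**Working it through.** **1. Is a final count by treatment specified anywhere?**

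| Place | What it gives | Final renal or hearing count by treatment? |
|---|---|---|
| 6.1.1 | Continuous comparisons; urine MTX against its solubility limit | No. The solubility check classifies a drug concentration, not a toxicity |
| 6.1.2 | Graded tables by treatment | No. Both toxicities are excluded |
| 5.2 with 5.4 | Delays, missed doses and dose modifications, by cycle | Indirect only; not by cause |
| 5.4 and 6.3 | Review of toxicity by treatment | After the first 12 patients only |
| 8 and 8.3 | CTCAE v.4 grading; eCRF capture of related events of grade 2 or higher | Data are captured, but no table by treatment is specified |

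**2. Which collected values go unused?**
- Serum creatinine is drawn at the end of each HDMTX infusion, at hour 24, and daily until MTX is below 0.1 mcM (Schedule of Study Procedures, footnote 3). Section 5.3 mentions a 24 h creatinine comparison, but 6.1.1 uses only pre-dose and 7-day values for GFR.
- A creatinine rise of at least 50% (Section 5.1; Schedule, footnote 10) triggers an extra sample and is never counted.
- Hearing at 2 kHz lies outside the 4-8 kHz average, so no audiogram comparison uses it.

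**3. The plan's own power figures.** The contrast of k measures per condition has variance SD²(1−ρ)(2/k). With 24 patients, 23 df and two-sided alpha 0.05:
- Pantoprazole (k = 2): 80.4% at 0.60 SD with ρ = 0; 79.6% at 0.42 SD with ρ = 0.5.
- HDMTX (k = 4): 79.6% at 0.42 SD with ρ = 0; 80.4% at 0.30 SD with ρ = 0.5.

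All match the stated 80%. All concern mean differences; no precision is given for an incidence.

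**4. What a count could show.**
- Denominators: 24 × 4 = 96 infusions per duration; 24 × 2 = 48 cisplatin courses per condition.
- At the 5% delayed-excretion rate, 96 × 0.05 = 4.8 events are expected.
- At 1.8%, 24 × 0.018 = 0.43 events if the unit is the patient (chance of none 0.982²⁴ = 65%), or 96 × 0.018 = 1.7 if it is the infusion. Section 1.3.2.1 does not state the unit.
- Exact two-sided 95% upper limits, ignoring clustering: 0/24 gives 1 − 0.025^(1/24) = 14.2%; 0/96 gives 3.8%.

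**5. Illustration (assumed inputs, not protocol data).** Suppose 5% of 4 h infusions cause a 50-point fall in GFR as a percentage of the pre-dose value, and no 12 h infusion does.
- Mean difference: 0.05 × 50 = 2.5 points.
- Variance of one patient's difference: (SD² + 50² × 0.05 × 0.95)/4 + SD²/4 = (2·SD² + 118.75)/4.
- SD 10: 318.75/4 = 79.7; standard error √(79.7/24) = 1.82; ratio 2.5/1.82 = 1.37.
- SD 15: 142.2; 2.43; 1.03.
- SD 20: 229.7; 3.09; 0.81.
- Simulated power of a paired t test on patient means (20,000 runs): 24%, 16% and 12%.
- About 5/96 against 0/96 would be counted: 5.2% (exact 95% interval 1.7-11.7%) against 0% (0-3.8%). Fisher's exact test gives p = 0.059, ignoring clustering, so the count would not be conclusive either. Its value is that it shows the pattern.

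**The case against.** Continuous endpoints are a declared choice: the synopsis and Section 3.1 explain that they keep the trial small in a rare cancer. The exclusions in 6.1.2 can be read as sending nephrotoxicity and ototoxicity to 6.1.1, where they are primary. For cisplatin the choice suits the problem, since Section 1.3.2.2 gives a mean GFR fall of 8% per dose and Section 1.3.4 says a substantial fraction of patients lose hearing. The continuous measures serve severity in part, and the urinary markers at 24 h do address acute HDMTX injury. Threshold crossings that are acted on enter the 5.4 data as delays or dose modifications. All of this stands, but none of it gives an incidence.

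A reader might go further and infer that these toxicities are dropped, that no such event will ever be recorded, or that the primary analysis is invalid. The documents do not support that. Both toxicities are primary, related events of grade 2 or higher are captured, the interim review covers them, and the power figures reproduce. A reader might also take 12-24% as the trial's power. It is not: the 5% is a delayed-excretion rate from 15 osteosarcoma and 45 leukaemia or lymphoma patients, and the 50-point fall, the zero rate at 12 h and the SDs are assumed.

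Counts have a weakness of their own. Cisplatin toxicity is cumulative and only partly reversible (Sections 1.3.2.2 and 1.3.4), so crude counts would mix treatment with period. The fix has to allow for that.

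**Conclusion.** The point holds as a gap in planned analysis and reporting, not in data collection. Sections 6 and 8 promise an incidence that no final analysis delivers, and collected values that could show acute renal events, or hearing at the 2 kHz level that governs cisplatin, enter no treatment comparison in 6.1.1. It should be corrected, but it does not threaten the primary inference. The textual finding rests on no assumption; the power illustration rests wholly on assumed event rates and SDs and shows only that a mean can miss a concentrated effect. Any counts would be descriptive and imprecise.

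**What to change.** Delete the two exclusions in Section 6.1.2. As descriptive support to the unchanged continuous primary analyses, tabulate the following for cycles 1-4, by HDMTX infusion duration and by cisplatin with or without pantoprazole:

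- CTCAE v.4 creatinine grade, and a creatinine rise of at least 50% over the pre-dose value, using the end-of-infusion, 24 h and daily values already drawn for HDMTX;
- CTCAE v.4 hearing grade per audiogram interval;
- crossings of the existing creatinine and 2 kHz hearing thresholds in Section 3.1.5.

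Give counts of patients and of doses or courses, with patient-clustered or exact intervals. Split them by period (cycles 1-2 and 3-4). Include patients who are later replaced under Sections 3.2 and 3.3.2, since replacement could otherwise remove those whose treatment ended early through toxicity.

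The cost is SAP wording and a few tables, plus keeping the 2 kHz threshold in the dataset beside the 4-8 kHz mean. No new tests are needed. The intervals will be wide: with 12 patients per condition in each period, 0/48 infusions has an upper limit of 1 − 0.025^(1/48) = 7.4% before clustering. The minimum alternative is to remove the word incidence from Sections 6 and 8, which makes the text consistent but gives up the information.
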